3) brace prescription (measured by the percentage of participants prescribed a brace after 1 year)

Background:

Adolescent idiopathic scoliosis (AIS) is a three-dimensional deformity of the spine, affecting 1-3% of children ages 10-16 years.¹ Adolescents with AIS have the highest risk of curve progression during the period of rapid growth prior to achieving skeletal maturity.¹ Patients who are Risser 0 are at greatest risk for curve progression.² The standard medical management for AIS in the United States (US) includes observation for skeletally immature mild curves, bracing for skeletally immature moderate curves, and surgery for severe curves.

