Recent, growing evidence supports the role of SSE methods to treat AIS. Systematic reviews (SR) conclude that exercises may be effective in reducing curve progression and reducing brace prescription.^{14,19} The evidence guality in the aforementioned reviews is low, with only one randomized controlled trial (RCT) included. Many of the studies are retrospective and most lack controls. Since the most recent SR, two recently published RCTs found SSE effective in reducing curve progression. One RCT of SSE consisted of SEAS (Scientific Exercise Approach to Scoliosis) in mild AIS compared to PT exercises that were not scoliosis-specific.²¹ A significantly improved Cobb angle in the SSE group was found immediately after treatment (at skeletal maturity) and at 1 year of follow-up post-treatment.²¹ The second RCT compared three groups of patients with AIS curves 10-60°: a supervised outpatient Schroth group, unsupervised home exercise Schroth group and a control group.²² At 24-weeks of follow-up, the Cobb angle improved in the supervised Schroth group but worsened in the other 2 groups.²² Another prospective controlled cohort study of SSE (Scientific Exercises Approach to Scoliosis) in mild AIS curves reported that brace prescription and curve progression were both significantly reduced compared to PT exercises that were not scoliosis-specific after 1 year of follow-up.²⁷ Brace prescription in patients was 6.1% in the SSE group compared to 25.0% in the non-SSE group. Curves improved in 23.5% and worsened in 11.8% of the SSE group compared to the non-specific exercise group in which 11.1% improved and 13.9% worsened.²⁷ Furthermore, a study of SSE (Schroth method) in children with idiopathic scoliosis reported significantly reduced curve progression in patients receiving intensive scoliosis in-patient rehabilitation compared to untreated patients.²⁴ Another study of the Schroth method described 50 patients with AIS treated on an out-patient basis for 4 hours a day, 5 days a week, for 6 weeks, followed by continued therapy at home. The average Cobb angle decreased from 26.1° pre-treatment to 23.5° at 6 weeks, 19.3° at 6 months, and 17.9° at 1 year.²⁵

The clinical management of patients with mild scoliosis remains controversial. Although various conservative strategies have been proposed, there is no consensus in the literature on the optimal treatment. High-quality evidence for the Schroth-based method is Current Protocol 4.19.2019.docx

Page 3 of 13

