lacking. Given the persisting uncertainty among medical professionals regarding the true potential of SSE, the purpose of this trial is to objectively and rigorously evaluate SSE compared to observation (standard-of-care). The results from this trial will provide much needed high-quality evidence regarding the feasibility and efficacy of SSE. In particular, this study will limit the inclusion criteria to skeletally immature patients with mild AIS curves. These patients are at highest risk of curve progression and have a greater potential for a meaningful effect with early intervention before their growth spurt and curve acceleration phase. Many families hope to avoid the need for bracewear.⁸ A smaller curve is more flexible²⁸ and may be more amenable to changes from exercise, especially before spinal growth is complete. In particular, mechanical wedging of the immature disc and vertebral body may still be reversible.²⁹

Concise Summary of Project:

This study will be a multi-center, dual-arm randomized control study evaluating skeletally immature patients with mild AIS curves. At six institutions, patients will be randomized into either the scoliosis-specific exercise (SSE) treatment arm or a control group. The SSE group will receive training in SSE, posture, and activities of daily living by physical therapists certified in Schroth-based exercise methods. The control group will not receive SSE instruction and will only be observed by their treating orthopaedic surgeon (which is considered the standard-of-care treatment method). Results will be compared after one year of treatment.

Study Procedures:

All patients with AIS meeting the following inclusion criteria will be eligible to participate in this trial: diagnosis of AIS; ages 10 to 17 years; major curve Cobb angles 12° to 24°; thoracolumbar, lumbar, or primary thoracic curve patterns; and Risser grade 0. Patients will be excluded according to the following exclusion criteria: scoliosis other than AIS, upper thoracic or double curve patterns, developmental disorders that prevent understanding and compliance with an exercise schedule, current or previous brace wear, and previous participation in a SSE program, previous spine surgery, inability to commit to performing a home exercise program for 15 minutes a day, 5 days a week, and inability to commit to attend at least 8 hours of PT within 6 months.

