All patients diagnosed with Adolescent Idiopathic Scoliosis who meet the following inclusion criteria will be eligible to participate in this trial:

- 1) Age 10 to 17 years
- 2) Major curve Cobb angles of 12° to 24°
- 3) Compensatory curve should be less than 5° of the main curve (ex: 10° if the main curve is 15° or 15° if the main curve is 20°)
- 3) Risser Grade 0
- 4) Single thoracic, thoracolumbar, or lumbar curve patterns

Criteria for Exclusion of Subjects:

Patients will be excluded according to the following exclusion criteria:

- 1) Scoliosis other than AIS (congenital, neuromuscular, etc)
- 2) Upper thoracic or double curve patterns
- 3) Diagnosis of a developmental disorder that prevents understanding and compliance with an exercise schedule
- 4) Current or previous brace wear
- 5) Previous participation in a SSE program
- 6) Previous spine surgery
- 7) Patient inability to commit to attend at least 8 hours of PT within 6 months

Sources of Research Material:

Current Protocol 4.19.2019.docx Page 7 of 13 After the consenting process, patient demographics will be collected from the patient chart. All demographic information, clinical, and radiographic measurements will be recorded after informed consent is obtained during the patient's appointments.

Texas Scottish Rite Hospital will serve as the lead institution for this study and will create/maintain a REDCap database to house all study data. All other participating sites will obtain IRB approval from their own institutions and will enter into a Data Use Agreement contract with Texas Scottish Rite Hospital in order to access the database and run data analysis. Only a limited data set will be shared between the institutions, and all patient information will be entered into the database in a de-identified fashion. The data to be shared between institutions includes:

- Patient study number (to be generated for each institution in a de-identified format through REDCap)
- Date patient is consented to the study
- Date physical therapy/control status is initiated
- Age
- Initial curve Cobb angles
- Risser sign
- De-identified x-ray images (AP and Lateral views)
- Height, Weight, and BMI
- Physical activity level
- Curve pattern (classification as thoracic, thoracolumbar, or lumbar)
- Schroth curve pattern
- Trunk rotation
- Triradiate status
- Menarchal status
- SRS-22
- 3 question parent survey about attitudes toward SSE, posture, and scoliosis

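### Brace prescription is an unmasked decision with no stated criterion and no Cobb angle at prescription, so deferred bracing in exercising patients could look like an effect on the curve

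*Combined protocol and SAP*

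**What the plan says.** Purpose, Aim 2, lists three effect outcomes: curve magnitude, progression of more than 5°, and "brace prescription (measured by the percentage of participants prescribed a brace after 1 year". I read the last as prescribed by the 1-year assessment. Anticipated Results predicts a significant reduction in each, under the statement that SSE will be effective. Biostatistics assigns categorical variables to Fisher's exact test.

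No section says what makes a prescription due. The nearest text is the Background account of US practice, "bracing for skeletally immature moderate curves, and surgery for severe curves", which puts no figure on moderate and is not a trial rule.

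Under Study Procedures the SSE arm receives supervised training and home exercise. The control arm is observed without treatment. Clinic visits and x-rays are standard of care under the treating physician. No masking of patient, surgeon or film reader is described anywhere. Background also says: "Many families hope to avoid the need for bracewear".

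Sources of Research Material lists the data shared between institutions. It has "Initial curve Cobb angles" and de-identified x-ray images with no time point. It does not list brace prescription, its date, the Cobb angle at prescription, or the 1-year Cobb angle.

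**The concern.** A prescription depends on the curve and on the willingness of surgeon and family to brace now rather than wait. Both know the arm. In the SSE arm an active treatment is already under way, which is a reason to wait. In the control arm there is none. With no stated criterion, nothing in the plan separates a curve that did not reach the point of bracing from one that reached it and was not braced.

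A lower prescription rate in the SSE arm would naturally be read as exercise controlling the curve, and the protocol predicts exactly that result. Deferral would push the comparison the same way. Masked reading of the films would not by itself protect this outcome, because the event counted is the prescription.

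**Working it through.** The protocol gives no sample size, power, significance level or effect size for this outcome, so there is no planned figure to reproduce. The check asks how far deferral alone could move the planned test.

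**Inputs from the protocol**
- Six sites (Concise Summary of Project: "At six institutions, patients will be randomized into either the scoliosis-specific exercise (SSE) treatment arm or a control group").
- At least 18 participants per site after 1 year (Anticipated Results). This is a feasibility benchmark, not a powered sample size.
- 2:1 allocation, blocked within site (Recruitment Methods and Consenting Process).
- Fisher's exact test (Biostatistics).

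**Assumptions**
- Two-sided 0.05 level; the protocol states neither level nor sidedness.
- A share q = 25% of each arm has a curve that would ordinarily lead to a brace. The size is borrowed from the non-SSE brace rate quoted in Background. 40% is also tried.
- A share w of qualifying SSE patients is not prescribed a brace because they are exercising. The documents give no value for w, so a range is shown.
- No effect of SSE on the curve.

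**Step 1, arm sizes.** 18 × 6 = 108; SSE 108 × 2/3 = 72; control 108 × 1/3 = 36.

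**Step 2, prescription rates.** Control rate = q. SSE rate = q × (1 − w).

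**Step 3, rejection probability.** Sum the product of the two binomial probabilities (36 at q, 72 at q(1 − w)) over all tables where Fisher's p ≤ 0.05.

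| w | SSE rate, q = 25% | Difference (points) | Rejects, q = 25% | Rejects, q = 40% |
|---|---|---|---|---|
| 0 | 25.0% | 0 | 3.7% | 3.8% |
| 1/6 | 20.8% | 4.2 | 6.3% | 8.0% |
| 1/3 | 16.7% | 8.3 | 14.7% | 25.4% |
| 1/2 | 12.5% | 12.5 | 32.1% | 55.3% |
| 3/4 | 6.25% | 18.75 | 73.0% | 93.2% |

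Once deferral is present, nearly all rejections favour SSE. At q = 25% and w = 1/3, for example, 14.6 of the 14.7 percentage points do.

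**Step 4, do differing site habits matter?** Six sites were simulated with 6 control and 12 SSE patients each. Baseline Cobb was uniform on 12–24°, the 1-year change Normal with mean 5° and SD 5° in both arms, and the site thresholds ranged from 20° to 30° but were the same for both arms within a site. These are modelling values only, not clinical rules. The mean arm difference was 0.00 and Fisher's test rejected in 2.5% of trials. Site variation does not by itself create an arm difference.

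**The case against.** **Aim 2 already has two curve outcomes.** A brace difference without a curve difference would show up beside the 1-year Cobb and the more-than-5° results. This stands in part. No masked reading is described for either outcome, and a brace fitted before 1 year may alter the 1-year Cobb. If controls are braced sooner, the cross-check itself is disturbed.

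**The sizes are assumed.** This stands. With one sixth deferred, rejection rises only from 3.7% to 6.3%; high rates need much larger deferral. The direction follows from the design, the amount does not.

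**The trial is preliminary and its primary aim is feasibility.** This stands, and it limits the weight of the point. Brace prescription is also a legitimate outcome that families care about.

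Three stronger readings are tempting and should not be drawn.

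1. *The cited cohort demonstrates the mechanism.* Background reports "Brace prescription in patients was 6.1% in the SSE group compared to 25.0% in the non-SSE group", a gap of 25.0 − 6.1 = 18.9 points. Worsening was 11.8% with SSE, and in the comparator "11.1% improved and 13.9% worsened", a gap of 13.9 − 11.8 = 2.1 points. But Background says prescription and progression were both significantly reduced, and improvement differed by 23.5 − 11.1 = 12.4 points. The comparator also exercised, so being in an exercise programme cannot alone explain the gap. The study was a cohort, not a randomized trial.
2. *The lead site could not compute the outcome.* The shared-data list omits it, but that list is introduced as what the data include and may not be exhaustive. The database is said to hold all study data, and Study Procedures intends brace prescription to be recorded during tracking to maturity. The list needs reconciling; it does not prove that the item is not collected.
3. *Different criteria at six sites bias the comparison.* Blocking within site prevents this, as Step 4 shows.

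**Conclusion.** The concern holds in this form: an unmasked decision, with no stated criterion and no Cobb angle recorded at prescription, can produce an arm difference in bracing with no effect on the curve. At 36 against 72 patients with 25% qualifying, the chance of a significant result rises from 3.7% to about 6%, 15% and 32% with one sixth, one third and one half deferred. These figures rest on assumed deferral shares, an assumed qualifying rate, a two-sided 0.05 level, and enrolment at the feasibility benchmark.

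A reader might infer that prescribing bias is expected, or that it explains earlier findings. The documents support neither. They show only that the plan could not tell such bias from a curve effect on this outcome. For a secondary outcome in a preliminary trial this is a change worth making, not a fatal flaw.

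**What to change.** 1. Keep brace prescription as an outcome.
2. Reconcile the shared-data list in Sources of Research Material with the Aim 2 outcomes. Add brace prescribed (yes/no), date of prescription, and Cobb angle and Risser grade at prescription. Confirm that follow-up films, including the one at the prescribing visit, are among the shared images.
3. Have the sponsor set down in advance, for analysis only, what on film it takes "bracing for skeletally immature moderate curves" to cover. The choice of figure is the sponsor's.
4. Report by arm the percentage whose film meets that definition by 1 year, whether or not a brace was prescribed. Since the images are de-identified, they can be read with the arm concealed.
5. Claim that SSE reduces the need for bracing only if both the prescription rate and the film measure support it. If only the first does, report a difference in prescribing.

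Patient care is unchanged. The cost is four data fields, one definition, one further table and the film reading. The brace result may look less favourable to SSE. One limit remains: a patient braced early may be kept below the film definition by the brace. The Cobb angle and date at prescription let such cases be counted.

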The University of Texas Southwestern Medical Center at Dallas Institutional Review Board

PROJECT SUMMARY

Principal Investigator:

[name], PT, DPT, PhD

Study Title:

Scoliosis-Specific Exercises for At-Risk Mild AIS Curves: A Multi-Site Preliminary Randomized Trial

Sponsor/Funding Source:

Scoliosis Research Society

Purpose:

To investigate the feasibility and short-term effectiveness of scoliosis specific exercises as part of a multi-center randomized controlled trial in patients with mild AIS curves at the greatest risk of progression. Specifically, our study aims are as follows:

Aim 1: The primary aim is to assess the feasibility of a multi-site prospective randomized controlled trial in skeletally immature patients with mild AIS curves at high risk of progression. Participants instructed in scoliosis-specific exercises (SSE) provided by physical therapists certified in the Schroth-based method (SSE group) will be compared to the standard-of-care of observation (control group).

Feasibility will be evaluated according to participant:

1) recruitment rate at each site (measured by the number of participants enrolled per month at each site)

2) overall recruitment rate (measured by the total number of participants enrolled after 1 vear)

3) treatment attendance in the SSE group (measured by the percentage of prescribed hours of physical therapy sessions attended)

4) home exercise adherence in the SSE group according to weekly e-mails (measured by the percentage of prescribed exercises completed from baseline to 1 year)

5) home exercise adherence in the SSE group according to a smartphone application (measured by the percentage of prescribed exercises completed from baseline to 1 vear)

6) home exercise adherence in the SSE group according to an exercise log (measured by the percentage of prescribed exercises completed from baseline to 1 year)

Aim 2: The secondary aim is to assess whether scoliosis-specific exercises (SSE) will be more effective in skeletally immature patients with mild AIS curves at high risk of progression, Current Protocol 4.19.2019.docx

Page 1 of 13

compared to the standard-of-care of observation (control).

The outcome quantifying the effect of 1 year of physical therapy intervention will include:

1) curve magnitude (measured by the Cobb angle on radiograph at baseline and 1 year)

2) curve progression (measured by whether the curve progresses >5° after 1 year)

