3) Proficiently perform a minimum of 8 exercises integrating scoliosis-specific corrections which include auto-elongation to increase the spaces between the pelvis, vertebrae, and ribs. Various kinesthetic, mental imagery and proprioceptive strategies are used to further open concavities and depress convexities.

4) Perform scoliosis-specific corrections during activities of daily living. The overall goal is for patients to maintain a corrective posture throughout the day.

Patients will be asked to use a smartphone or tablet application (app) when performing the home exercise program which will be one method of tracking exercise adherence. A paper version of the app will be available to patients without access to a smartphone or tablet. Patients will also be sent electronically via email that is collected with a demographic intake form on the patient's initial visit, a weekly survey regarding home exercise adherence through a secure research database, the Research Electronic Data Capture (REDCap). An exercise log initialed by the guardian will help families keep track of their exercise adherence and serve as a way to monitor exercise adherence for patients who may not have a smartphone, tablet, or computer.

Current Protocol 4.19.2019.docx Page 5 of 13 Patients will also be able to meet with the therapists at their return-to-clinic visits and every 2-3 months thereafter until their 1 year follow-up to assess performance quality, maintain motivation, and progress intensity. Patients may be withdrawn if they do not maintainexercise adherence within 6 months.

B) Control Group

Patients randomized to this group will continue receiving standard-of-care treatment from their orthopaedic physician which includes regularly scheduled clinic visits and observation. Observation consists of no treatment of the scoliosis, only routine clinical assessment by the orthopaedic surgeon to detect curve progression every 3 to 6 months.

Once all measurements have been collected at the patient's enrollment and one year followup, patients in this group will continue to be tracked through observation until skeletal maturity in order to record whether the patient experienced curve progression, was prescribed a brace, or proceeded to surgical treatment.

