Patients randomized to the exercise group who never initiate physical therapy (do not attend even one session of physical therapy or begin a home exercise program) may be switched to the control group and observed in the same manner.

3) Outcome measures

Patients and their legal guardians will be asked to fill-out three self-reported outcome scores at their initial appointment and 1 year post the initiation of their participant in the study. The questionnaires to be completed include:

SRS-22:

The survey is a valid instrument for the assessment of the health related quality of life of patients treated for idiopathic scoliosis. This Heath Related Quality of Life (HRQL) questionnaire is designed to assess the effect that idiopathic scoliosis has on the patient in regards to pain, activity level, medications used, and satisfaction with treatment to date, and mental health status. The SRS-22 is one of the frequently tested scoliosis questionnaires and has been shown to have high levels of both reliability and validity.

Patient and parent survey:

A 3 question survey (one for patient, one for parent) that asks patients and parents questions regarding their/the child's attitudes toward SSE, their/their child's posture, and their/their child's scoliosis.

Once all measurements have been collected at the patient's enrollment at and one year follow-up, patients in this group will continue to be tracked through observation until skeletal maturity in order to record whether the patient experienced curve progression, was prescribed a braced, or proceeded to surgical treatment.

Current Protocol 4.19.2019.docx Page 6 of 13 While the SSE training will be considered for research purposes only, all regularly scheduled clinic visits with the patients' treating physicians and x-rays will be considered standard-of-care.

Anticipated Results:

We predict that at one-year follow-up:

I. A multi-site prospective randomized controlled trial in skeletally immature participants with mild AIS curves at high risk of progression is feasible as evidenced by acceptable participant recruitment rates (\geq 18 participants per site after 1 year), treatment attendance (\geq 80%), and home exercise adherence.

II. Scoliosis-specific exercises will be effective and will demonstrate:

- 1) Significantly smaller change in curve magnitude
- 2) Significantly reduced incidence of curve progression
- 3) Significantly reduced incidence of brace prescription

Criteria for Inclusion of Subjects:

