Eligible patients will be screened based on the research coordinator's review of the scoliosis clinics at TSRH or from the recommendation of the patient's treating physician. The Investigators in this study will have the ability to suggest their own patients. Once deemed eligible, a member of the study team will meet with the patient and his or her legal guardians in order to review the consent form. The patient and family will be given ample time to review the consent form and ask any questions. In order to respect the privacy of potential patients, all consenting procedures will occur in a private clinic exam room. The research coordinator will explain to the family that their participation in the study is voluntarily and they will receive their participation (or lack of) in the study will not affect their standard treatment or relationship with their treating physician. Appropriate patient assent and caregiver consent will be obtained by a member of the study team prior to any study activities occurring (per IRB protocol) Patients meeting the study criteria who consent to participate will be randomly assigned to either the treatment or control arm in a 2:1 ratio. Patients will be assigned a group using a block-randomized, within site method. Patient assignment will be done by utilizing a computer-generated list and pre-sealed envelopes that will be distributed to the participating sites before enrollment. The list and envelopes will be generated by the statistician at Texas Scottish Rite Hospital.

If an eligible patient is missed in clinic whom the research team has an existing relationship with through a medical staff member on the study team, they may be contacted by a member of the research team via phone. The patient family will be identified and then told the following:

Schroth Ex-Trial Phone Solicitation Script:

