All information obtained through medical and radiographic records will be reviewed solely by the primary investigators, co-investigators, and other study team personnel. Publically reported information will be in the form of a statistical summary only: no information will be divulged that could be linked to a specific patient involved with the study. No patient information will be disclosed outside of the study team. The University of Texas Southwestern Medical Center Institutional Review Board may review the research information for auditing purposes. The team will keep the consents and study files in both a locked cabinet as well as electronic copies within the electronic study folder (this folder will be stored on password encrypted hard drive which may be accessed by members of the study team only). All other electronic data collected will be stored on a password protected electronic database with access limited to the study team.

Procedures to Maintain Confidentiality:

All normally used means for protecting patient confidentiality will be strictly followed. All consents, clinical and radiographic measurements, and patient demographics will be stored in a secure electronic database. This database will be password protected and access will be limited to only individuals on the study team. Data will be de-identified for each patient by assigning a Study ID in the database. All PHI and the unique study ID for each patient will be stored in a separate password-protected and encrypted spreadsheet that only members of the study team at TSRH will have access to. Only a statistical summary of the information will be published: at no time will any data published include information that can be linked to a study participant. All requirements for HIPAA compliance in regards to patient confidentiality will be followed and the University of Texas Southwestern Medical Center's Institutional Review Board will have the right to inspect all medical records related to this study for the purpose of ensuring patient confidentiality.

Current Protocol 4.19.2019.docx Page 10 of 13

Biostatistics

Continuous variables will be summarized with means, standard deviations and ranges and analyzed using student t-tests; categorical variables will be summarized as counts and percentages and analyzed using Fischer's exact tests. Data will be checked for normality and equal variance.

Potential Benefits:

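### SSE patients can be withdrawn for poor adherence or moved to control, with no follow-up or analysis rule, so Aim 1 adherence can be inflated and the 1-year comparison can lose patients from one arm

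*Combined protocol and SAP*

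**What the plan says.** Aim 1, the primary aim, is feasibility. Three of its six measures (items 4 to 6) are home exercise adherence in the SSE group, taken from weekly e-mails, a smartphone application and an exercise log. Each is "measured by the percentage of prescribed exercises completed from baseline to 1 year". Item 3 is the percentage of prescribed physical therapy hours attended. Under Anticipated Results, item I, the trial "is feasible as evidenced by acceptable participant recruitment rates" of at least 18 per site after 1 year, attendance of at least 80%, and home adherence, for which no number is given.

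Two rules change a patient's status after randomisation, and both apply only to patients assigned to SSE:

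- Study Procedures, 2) Study Groups, A) SSE Group: "Patients may be withdrawn if they do not maintainexercise adherence within 6 months".
- Study Procedures, 2) Study Groups, B) Control Group: patients assigned to exercise who attend no session and begin no home programme "may be switched to the control group and observed in the same manner".

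Patients are "randomly assigned to either the treatment or control arm in a 2:1 ratio" (Recruitment Methods and Consenting Process). The Biostatistics section says: "Continuous variables will be summarized with means, standard deviations and ranges and analyzed using student t-tests", with Fisher's exact tests for categorical variables and a check of normality and equal variance. It contains no analysis set, no statement that patients are analysed as randomised, and no rule for missing data.

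**The concern.** The trigger for withdrawal is the quantity that Aim 1 sets out to measure. If patients who fail it leave the data, reported adherence describes only those who passed. Removing the lowest adherers can only raise the mean, whatever their prognosis. A larger trial planned on that figure would be planned on the wrong one.

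The switch does similar damage to attendance. A patient who never starts has attended 0% of the prescribed hours. Counting that patient as a control removes a zero from the SSE denominator, and attendance is the only SSE-arm feasibility measure with a numeric pass mark.

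For Aim 2 (Cobb angle, progression of more than 5°, brace prescription), the withdrawal rule removes patients from one arm on the basis of behaviour after randomisation. The switch, if followed in the analysis, also changes the control group. In either case the groups compared are no longer those formed by randomisation.

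Non-adherence is a realistic prospect. The Background cites an earlier US exercise study in which 4 of 41 subjects (9.8%) reported compliance and no conclusion on effectiveness could be drawn.

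**Working it through.** The documents state no sample size, alpha, power or dropout rate, so there is no plan figure to reproduce. What follows is illustration.

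**Inputs.** Six sites (Concise Summary of Project) × 18 per site (Anticipated Results) = 108. At 2:1 this is 72 SSE and 36 control. This is the recruitment criterion multiplied out, not a planned sample size. The progression risks of 50% and 38% come from the Background. They are loosely matched: the 50% is for progression of at least 5° at Risser 0 to 1 with curves of 15–30°, and the 38% is for progression of at least 10°. Neither has a stated 1-year horizon. Shares withdrawn, adherence levels, risk gaps and a two-sided alpha of 0.05 are assumptions.

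**1. Home adherence.** Let f be the share of SSE patients withdrawn, with retained patients averaging 85% and withdrawn patients 20%. The all-randomised mean is f × 20 + (1 − f) × 85. The retained-only mean is always 85%.

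| f | All-randomised mean | Overstatement (points) |
|---|---|---|
| 10% | 78.5% | 6.5 |
| 20% | 72.0% | 13 |
| 30% | 65.5% | 19.5 |

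**2. Attendance with non-starters moved out.** Assume equal prescribed hours. If starters average 85%, then 85% is reported. Over all 72 patients:

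- 4 non-starters: 68 × 0.85 / 72 = 80.3%
- 5 non-starters: 67 × 0.85 / 72 = 79.1%, below the 80% criterion

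If starters average 95%, 11 non-starters give 61 × 0.95 / 72 = 80.5% and 12 give 60 × 0.95 / 72 = 79.2%.

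**3. Progression, with no true effect.** Let g be the progression risk in withdrawn patients minus that in retained patients. The retained SSE risk is then base − f × g, and control stays at base with n = 36. Rejection rates are by exact enumeration of the two-sided Fisher test.

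Base 50%; with nobody withdrawn (72 against 36) the rate is 4.0%:

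| Withdrawn (SSE n kept) | g = 0 | g = 10 points | g = 20 points | g = 30 points |
|---|---|---|---|---|
| 10% (65) | 3.8% | 3.8% | 4.1% | 4.5% |
| 20% (58) | 3.3% | 3.6% | 4.5% | 6.2% |
| 30% (50) | 4.3% | 5.1% | 7.6% | 11.9% |

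At base 38% with 30% withdrawn, gaps of 20 and 30 points give 7.5% and 12.2%.

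The two-sided rate understates the shift. At base 50%, rejections favouring SSE are 2.0% with nobody withdrawn. With 10% withdrawn they are 2.9% and 3.6% at gaps of 20 and 30 points; with 30% withdrawn they are 7.1% and 11.6%. If withdrawn patients have the better prognosis, the bias reverses.

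**4. Switch analysed as switched.** Suppose 7 of 72 are moved, with a 20-point higher risk and base 50%. The remaining SSE risk is 0.50 − (7/72) × 0.20 = 0.481, and the switched patients' risk is 0.681. The enlarged control group has (36 × 0.50 + 7 × 0.681) / 43 = 0.529. The spurious difference is 4.9 points. With no gap in risk it is zero.

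**The case against.** The strongest reply is that the text is silent and does not plan any exclusion. Withdrawal is discretionary, the protocol does not say the data are discarded, and a measure in the SSE group can be read as covering everyone assigned to it. Switched patients are explicitly still observed. Visits and films exist in any case, since "all regularly scheduled clinic visits with the patients' treating physicians and x-rays will be considered standard-of-care". Pages removed from the public copy might say what follows a withdrawal. Screening patients for commitment to the programme may keep the numbers small. The withdrawal rule flips no stated criterion, because home adherence has no threshold; the calculation that crosses 80% belongs to the switch. The efficacy distortion is slight unless many patients are withdrawn, and efficacy is a secondary aim of a preliminary trial.

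Much of this limits the size of the harm, and is accepted as such. It does not supply the missing rule. A discretion with no threshold, exercised at six sites, may be applied differently at each. Radiographs may exist, but nothing commits the study to using them for withdrawn patients. The tracking to skeletal maturity begins only after the enrolment and 1-year measurements are complete, so it does not secure the 1-year data. The adherence distortion needs no assumption about prognosis and falls on the primary aim.

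There is also a fair point of definition. Counting exercise as not completed after the study has withdrawn a patient treats it as still prescribed. Reporting adherence up to withdrawal, with withdrawal counts, is another defensible measure. The first fits better with a measure defined from baseline to 1 year, and the second can be shown beside it.

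**Conclusion.** The concern holds and should be fixed before analysis. The plan contains two post-randomisation rules that act only on SSE patients, and no follow-up or analysis rule to neutralise them.

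Confidence in the omission is high. The harm depends on how often the rules are used and on whether the affected patients leave the data or are analysed as switched. For adherence the direction is certain if low adherers are dropped, and the size depends on the assumed levels. Attendance can pass 80% wrongly with as few as 5 of 72 non-starters if starters average 85%, but it takes 12 if they average 95%. For the efficacy comparison, size and direction are unknown. On these assumptions, a two-sided error rate clearly above 5% needs about 20% withdrawn with a 30-point gap, or 30% withdrawn with a gap of 20 points or more. It adds no bias if adherence is unrelated to prognosis. The withdrawal and switch rules act on one arm; voluntary withdrawal can occur in either.

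**What to change.** Add an analysis rule to the Biostatistics section along these lines:

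> Non-adherence is recorded as an outcome and does not end follow-up. All randomised patients have 1-year radiograph and brace status recorded from standard-of-care visits and are analysed in the group to which they were assigned. Aim 1 adherence and attendance use all patients randomised to SSE; exercise or sessions not done after stopping, or never started, count as not completed. Patients who withdraw consent are reported as missing, with counts by arm.

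Then reconcile the withdrawal sentence in the SSE section and the switch in the Control Group section with this rule. Whether a patient continues therapy is a care decision and is not addressed here. An adherers-only analysis, or adherence up to the point of withdrawal, may be shown as supplementary.

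The cost is mainly wording. Visits and x-rays are already standard of care, and 1-year outcomes are already needed for Aim 2. Two small burdens remain. The 3-to-6-month visit interval is written only for controls, so sites should confirm that a 1-year film will be obtained for every patient. Each site also holds its own IRB approval, so the change must be circulated. Reported adherence and attendance may come out lower.
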